#### INFORMED CONSENT

Capable of giving signed informed consent as described in Section 10.2, which includes compliance with the requirements and restrictions listed in the consent form and in this protocol. Eligible participants or their legal guardians (and next of kin when locally required), must sign a written Informed Consent Form before any protocol-specified assessments are conducted. Enrolment of participants who are unable to provide direct informed consent is optional and will be based on local legal/regulatory requirements and site feasibility to conduct protocol procedures.

#### OTHER

**Participants enrolled in France** must be affiliated to, or a beneficiary of, a social security category.

**All participants** participating in the study should be counselled on safer sexual practices including the use and benefit/risk of effective barrier methods (e.g., male condom) and on the risk of HIV transmission to an uninfected partner.

## 5.2. Exclusion Criteria

Deviations from exclusion criteria are not allowed because they can potentially jeopardize the scientific integrity of the study, regulatory acceptability, or participant safety. Therefore, adherence to the criteria as specified in the protocol is essential. A participant will not be eligible for inclusion in this study if any of the following criteria apply:

#### Exclusionary Criteria prior to Screening or Day 1

1. Within 6 months prior to Screening and after confirmed suppression to <50 c/mL on current ART regimen, any plasma HIV-1 RNA measurement  $\geq 50$  c/mL
2. Within the 6 to 12 month window prior to Screening and after confirmed suppression to <50 c/mL, any plasma HIV-1 RNA measurement >200 c/mL, or 2 or more plasma HIV-1 RNA measurements  $\geq 50$  c/mL
3. Any drug holiday during the window between initiating first HIV ART and 6

months prior to Screening, except for brief periods (less than 1 month) where all ART was stopped due to tolerability and/or safety concerns
 
 
4. Any switch to a second line regimen, defined as change of a single drug or multiple drugs simultaneously, due to virologic failure to therapy (defined as a confirmed plasma HIV-1 RNA measurement <math>\geq 400</math> c/mL after initial suppression to <math>< 50</math> c/mL while on first line HIV therapy regimen)
 
5. Abacavir/dolutegravir/lamivudine, (ABC/DTG/3TC) as current ART regimen
 
6. A history of use of any regimen consisting of only single NNRTI therapy (even if only for peri-partum treatment), or only single or dual NRTI therapy prior to starting cART
 
7. Participants who are currently participating in or anticipate to be selected for any other interventional study
 

Exclusionary medical conditions


 
8. Women who are pregnant, breastfeeding or plan to become pregnant or breastfeed during the study
 
9. Any evidence of an active Center for Disease Control and Prevention (CDC) Stage 3 disease [CDC, 2014], except cutaneous Kaposi's sarcoma not requiring systemic therapy and historical or current CD4 cell counts less than 200 cells/mm^3
 
10. Participants with moderate to severe hepatic impairment
 
11. Any pre-existing physical or mental condition (including substance use disorder) which, in the opinion of the Investigator, may interfere with the participant's ability to comply with the dosing schedule and/or protocol evaluations or which may compromise the safety of the participant
 
12. Participants determined by the Investigator to have a high risk of seizures, including participants with an unstable or poorly controlled seizure disorder. A participant with a prior history of seizure may be considered for enrolment if the Investigator believes the risk of seizure recurrence is low. All cases of prior seizure history should be discussed with the Medical Monitor prior to enrolment
 
13. All participants will be screened for syphilis (rapid plasma reagin [RPR]). Participants with untreated syphilis infection, defined as a positive RPR without clear documentation of treatment, are excluded. Participants with a serofast RPR result (persistence of a reactive nontreponemal syphilis test) despite history of adequate therapy and no evidence of re-exposure may enrol after consultation with the Medical Monitor. Participants with a positive RPR test who have not been treated may be rescreened at least 30 days after completion of antibiotic treatment for syphilis
 
14. Participants who, in the investigator's judgment, pose a significant suicide risk. Participant's recent history of suicidal behavior and/or suicidal ideation should be considered when evaluating for suicide risk
 
15. The participant has a tattoo or other dermatological condition overlying the
 

gluteus region which may interfere with interpretation of injection site reactions

16. Evidence of Hepatitis B virus (HBV) infection based on the results of testing at Screening for Hepatitis B surface antigen (HBsAg), Hepatitis B core antibody (anti-HBc), Hepatitis B surface antibody (anti-HBs) and HBV DNA as follows:

- Participants positive for HBsAg are excluded;
- Participants negative for anti-HBs but positive for anti-HBc (negative HBsAg status) and positive for HBV DNA are excluded

*Note:* Participants positive for anti-HBc (negative HBsAg status) and positive for anti-HBs (past and/or current evidence) are immune to HBV and are not excluded.

17. Asymptomatic individuals with chronic hepatitis C virus (HCV) infection will not be excluded, however Investigators must carefully assess if therapy specific for HCV infection is required; participants who are anticipated to require HCV treatment within 12 months must be excluded. (HCV treatment on study may be permitted post Week 48, following consultation with the medical monitor)

Participants with HCV co-infection will be allowed entry into phase 3 studies if:

- Liver enzymes meet entry criteria
- HCV Disease has undergone appropriate work-up, and is not advanced, and will not require treatment prior to the Week 48 visit. Additional information (where available) on participants with HCV co-infection at screening should include results from any liver biopsy, Fibroscan, ultrasound, or other fibrosis evaluation, history of cirrhosis or other decompensated liver disease, prior treatment, and timing/plan for HCV treatment.
- In the event that recent biopsy or imaging data is not available or inconclusive, the Fib-4 score will be used to verify eligibility
  - Fib-4 score > 3.25 is exclusionary
  - Fib-4 scores 1.45 – 3.25 requires Medical Monitor consultation

**Fibrosis 4 Score Formula:**

$$(\text{Age} \times \text{AST}) / (\text{Platelets} \times (\text{sqr} [\text{ALT}]))$$

18. Unstable liver disease (as defined by any of the following: presence of ascites, encephalopathy, coagulopathy, hypoalbuminemia, esophageal or gastric varices, or persistent jaundice or cirrhosis), known biliary abnormalities (with the exception of Gilbert's syndrome or asymptomatic gallstones or otherwise stable chronic liver disease per investigator assessment)

19. History of liver cirrhosis with or without hepatitis viral co-infection.

20. Ongoing or clinically relevant pancreatitis

21. Clinically significant cardiovascular disease, as defined by history/evidence of congestive heart failure, symptomatic arrhythmia, angina/ischemia, coronary artery bypass grafting (CABG) surgery or percutaneous transluminal coronary angioplasty (PTCA) or any clinically significant cardiac disease

22. Ongoing malignancy other than cutaneous Kaposi's sarcoma, basal cell

carcinoma, or resected, non-invasive cutaneous squamous cell carcinoma, or cervical intraepithelial neoplasia; other localized malignancies require agreement between the investigator and the Study medical monitor for inclusion of the participant prior to randomization
 
23. Any condition which, in the opinion of the Investigator, may interfere with the absorption, distribution, metabolism or excretion of the study drugs or render the participant unable to receive study medication
 
24. History or presence of allergy or intolerance to the study drugs or their components or drugs of their class. In addition, if heparin is used during PK sampling, participants with a history of sensitivity to heparin or heparin-induced thrombocytopenia must not be enrolled
 
25. Current or anticipated need for chronic anti-coagulation with the exception of the use of low dose acetylsalicylic acid (<math>\leq 325</math>mg)


Exclusionary Laboratory Values or Clinical Assessments at Screening (a single repeat to determine eligibility is allowed)
 
26. Any evidence of primary resistance based on the presence of any major known INI or NNRTI resistance-associated mutation, except for K103N, (International AIDS Society [IAS]-USA, 2015) by any historical resistance test result.
 
Note: Prior genotypic resistance testing is not required but if available it must be provided to GSK, after screening and before randomization according to guidance in the SPM, to provide direct evidence of no pre-existing exclusionary resistance mutations. You must wait for the study virologists to confirm the lack of exclusionary resistance mutations, which will be provided before the screening window closes. Details regarding baseline or prior resistance data must be noted in the source documentation
 
27. Any verified Grade 4 laboratory abnormality. A single repeat test is allowed during the Screening phase to verify a result
 
28. Any acute laboratory abnormality at Screening, which, in the opinion of the investigator, would preclude the participant's participation in the study of an investigational compound
 
29. Participant has estimated creatine clearance <math>< 50</math> mL/min per <math>1.73</math> m^2 via CKD-EPI Method
 
30. Alanine aminotransferase (ALT) <math>\geq 3 \times</math> ULN

Concomitant Medications
 
31. Exposure to an experimental drug or experimental vaccine within either 30 days, 5 half-lives of the test agent, or twice the duration of the biological effect of the test agent, whichever is longer, prior to Day 1 of this study;
 
32. Treatment with any of the following agents within 28 days of Screening:
 
 
• radiation therapy;
 
• cytotoxic chemotherapeutic agents;
 

- tuberculosis therapy with the exception of isoniazid (isonicotinylhydrazid, INH);
  - anti-coagulation agents;
  - Immunomodulators that alter immune responses such as chronic systemic corticosteroids, interleukins, or interferons. Note: Participants using short-term (e.g.  $\leq 21$  days) systemic corticosteroid treatment; topical, inhaled and intranasal corticosteroids are eligible for enrolment.
33. Treatment with an HIV-1 immunotherapeutic vaccine within 90 days of Screening
  34. Treatment with any agent, except recognized ART as allowed above, with documented activity against HIV-1 within 28 days of study Day 1
  35. Use of medications which are associated with Torsade de Pointes. (See SPM for a list of relevant medications)
  36. Current or prior history of etravirine (ETR) use
  37. Current use of tipranavir/ritonavir or fosamprenavir/ritonavir
  38. Participants receiving any prohibited medication listed in Section 6.13.2 and who are unwilling or unable to switch to an alternate medication. Note: Any prohibited medications listed in Section 6.13.2 that decrease CAB or RPV concentrations should be discontinued for a minimum of four weeks or a minimum of three half-lives (whichever is longer) prior to the first dose and any other prohibited medications should be discontinued for a minimum of two weeks or a minimum of three half-lives (whichever is longer) prior to the first dose (see Section 6.13.2 for details of prohibited medications)

### 5.3. Additional Eligibility Criteria

To assess any potential impact on participant eligibility with regard to safety, the investigator must refer to the IB and supplements, approved product labels, and/or local prescribing information for detailed information regarding warnings, precautions, contraindications, AEs, drug interactions, and other significant data pertaining to the study drugs.

**Notwithstanding these minimum inclusion and exclusion criteria, investigators must also follow country specific guidelines where they exist when making decisions about participants who are eligible for study participation.**

### 5.4. Screening/Baseline/Run-in Failures

Screen failures are defined as participants who consent to participate in the clinical trial but are never subsequently randomized. In order to ensure transparent reporting of screen failure participants, meet the Consolidated Standards of Reporting Trials (CONSORT) publishing requirements, and respond to queries from Regulatory authorities, a minimal set of screen failure information is required including Demography, Screen Failure details, Eligibility Criteria, and Serious Adverse Events (see Section 7.4.3.2).

A single repeat of a procedure / lab parameter is allowed to determine eligibility (unless otherwise specified).

Participants are allowed to re-screen for this study one time. This will require a new participant number.

## **5.5. Withdrawal/Stopping Criteria**

Participants permanently discontinuing study treatments prior to the Week 52 visit are considered to be withdrawn from the study treatments. Participants who enter the Extension Phase but permanently discontinue participation in the Extension Phase prior to commercially available CAB LA + RPV LA are considered to be withdrawn from the study treatments but are not considered to be withdrawn from the study because they will enter the follow Follow-up Phase.

A participant may withdraw consent and discontinue participation in this study at any time at his/her own request. The investigator may also, at his or her discretion, discontinue the participant from participating in this study at any time (e.g., safety, behavioural or administrative reasons). If a participant withdraws from the study, he/she may request destruction of any samples taken, and the investigator must document this in the site study records. Withdrawn participants will not be replaced.

All participants who discontinue prematurely from the study, irrespective of arm, will be asked for additional information to establish the reason for withdrawal.

Participants are not obligated to state the reason for withdrawal. However, the reasons for withdrawal, or failure to provide a reason, must be documented by the Investigator on the Completion/Withdrawal section of the electronic case report form (eCRF). Every effort should be made by the Investigator to follow-up participants who withdraw from the study.

Participants may have a temporary interruption to their study treatment for management of toxicities.

**Participants may be prematurely discontinued from the study for any of the following reasons:**

- Adverse event / Serious adverse event
- Protocol deviation
- Intolerability of injections
- Participant lost to follow-up
- Participant or Investigator non-compliance;
- Termination of the study by the Sponsor
- At the request of the participant, Investigator, GSK or ViiV Healthcare;

- The participant requires concurrent prohibited medications during the course of the study. The participant may remain in the study if in the opinion of the Investigator and the medical monitor; such medication will not interfere with the conduct or interpretation of the study or compromise the safety of the participant.

**Participants must be discontinued from the study for any of the following reasons:**

- Participants who are not eligible to continue into the Maintenance Phase.
- Participants who are not eligible, or do not wish to continue on to the Extension Phase.
- Virologic withdrawal criteria as specified in Section 5.5.4 are met;
- For participants in the current ART arm during the Maintenance Phase, plasma HIV-1 RNA  $\geq 50$  c/mL at Week 48 with a confirmatory retest;
- Participant requires substitution or dose modification of current ART;
- Participant requires substitution or dose reduction of CAB LA or RPV LA (oral bridging supply and potential for a second loading dose may be permissible following discussion with the Medical Monitor).
- Liver toxicity where stopping criteria are met and no compelling alternate cause is identified (see Section 5.5.1);
- Renal toxicity are met and no compelling alternate cause is identified;
- QT interval (QTc) interval  $> 550$  msec from three or more tracings separated by at least 5 minutes and considered causally related to IP.
- Grade 4 clinical AE considered causally related to study drug;
- Participant has a Grade 3 or higher rash or Grade 2 rash with evidence of systemic involvement and no compelling alternative cause is identified
- Pregnancy (intrauterine), regardless of termination status of pregnancy.
- Participant withdrew consent

Efficacy data for participants withdrawing from the study will be considered evaluable up to the point at which they are withdrawn using the same criteria for evaluability as for participants who complete the study.

Safety data for all participants who receive any amount of study drug, including participants who withdraw from the study, will be included in evaluations of safety.

If a participant is prematurely or permanently withdrawn from the study, the procedures described in the Time and Events Table for the in-clinic Withdrawal visit are to be performed. An in-clinic Follow-Up visit will be conducted 4 weeks after the last dose of study medication for participants with ongoing AEs, and serious adverse events (SAEs)

related & not related to study drug and also any laboratory abnormalities that are considered to be AEs or potentially harmful to the participant, at the last on-study visit.

All data from the Withdrawal visit will be recorded, as they comprise an essential evaluation that should be done prior to discharging any participant from the study.

The following actions must be taken in relation to a participant who fails to attend the clinic for a required study visit:

- The site must attempt to contact the participant and re-schedule the missed visit as soon as possible.
- The site must counsel the participant on the importance of maintaining the assigned visit schedule and ascertain whether or not the participant wishes to and/or should continue in the study.
- In cases where the participant is deemed 'lost to follow up', the investigator or designee must make every effort to regain contact with the participant (where possible, 3 telephone calls and if necessary a certified letter to the participant's last known mailing address or local equivalent methods). These contact attempts should be documented in the participant's medical record.
- Should the participant continue to be unreachable, only then will he/she be considered to have withdrawn from the study with a primary reason of "Lost to Follow-up".

A participant may withdraw from study treatment at any time at his/her own request, or may be withdrawn at any time at the discretion of the investigator for safety, behavioural or administrative reasons. If a participant withdraws from the study, he/she may request destruction of any samples taken, and the investigator must document this in the site study records.

### 5.5.1. Liver Chemistry Stopping Criteria

**Liver chemistry stopping and increased monitoring criteria** have been designed to assure participant safety and evaluate liver event etiology (in alignment with the FDA premarketing clinical liver safety guidance).

<http://www.fda.gov/downloads/Drugs/GuidanceComplianceRegulatoryInformation/Guidances/UCM174090.pdf>

IP will be stopped if any of the following liver chemistry criteria are met:

- ALT  $\geq 3 \times \text{ULN}$  **and** bilirubin  $\geq 2 \times \text{ULN}$  (>35% direct bilirubin, bilirubin fractionation required).

NOTE: serum bilirubin fractionation should be performed if testing is available. If testing is unavailable, sites should evaluate **the presence of detectable urinary bilirubin on dipstick**, indicating direct bilirubin elevations and suggesting liver injury. If testing is unavailable and a participant meets the criterion of total bilirubin  $\geq 2 \times \text{ULN}$ , then the event meets liver stopping criteria.

- ALT  $\geq 8 \times \text{ULN}$ .

- ALT  $\geq 3$ xULN (if Baseline ALT is  $<$  ULN) with symptoms or worsening of acute hepatitis or hypersensitivity such as fatigue, nausea, vomiting, right upper quadrant pain or tenderness, fever, rash, or eosinophilia, OR;
- ALT  $\geq 3$ x Baseline ALT with symptoms or worsening of acute hepatitis or hypersensitivity such as fatigue, nausea, vomiting, right upper quadrant pain or tenderness, fever, rash, or eosinophilia;
- ALT  $\geq 5$ xULN and  $< 8$ xULN that persists  $\geq 2$  weeks (with bilirubin  $< 2$  ULN & no signs or symptoms of acute hepatitis or hypersensitivity).
- ALT  $\geq 5$ xULN but  $< 8$ xULN and cannot be monitored weekly for  $> 2$  weeks.

See Section 5.5.1.1 for Participant Management and Follow-Up.

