Drug Induced Liver Injury (DILIs)	
A small proportion of participants in the CAB program to date (total exposure approximately 1198 to 01 April 2016) have developed transaminitis (elevated liver transaminases characterised by predominant Alanine aminotransferase (ALT) elevation). In some of these participants' transient transaminitis were explained by acute hepatitis C infection whilst a small number of others did not have alternative explanations, suggesting a mild form of Drug induced liver injury (DILI) without hepatic dysfunction which resolved upon withdrawal of treatment with CAB.
 
Of the five participants with possible or probable cases of DILI identified in Phase 2 studies, four participants were receiving oral CAB and one participant developed probable DILI following CAB IM or Placebo IM administration.
	
 
• Exclusion criteria as described in Section 5.2 will prohibit participants with significant liver impairment based on screening liver chemistry including transaminases (ALT and Aspartate aminotransferase [AST]) as well on prior medical history. Participants with a history of chronic liver disease with ongoing inflammation and/or fibrosis will have additional confirmatory assessments to confirm suitability for entry into the study.
 
• A 4-week oral lead- in Phase is being implemented in this study, where all participants will receive oral CAB prior to the administration of IM CAB to determine individual safety and tolerability
 
• Liver transaminases (ALT and AST) will be closely monitored throughout this study (refer to Time & Events Table) and the liver chemistry stopping criteria will be adopted as described in Section 5.5.1.1 of this protocol. Participants will be withdrawn from CAB treatment where no compelling alternative cause is identified and DILI is suspected.
 
• Participants who develop ALT <math>\geq 3</math> times the upper limit of normal (ULN) while on study must consult with Medical Monitor prior to initiation or continuation of CAB LA + RPV LA.
 

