##### When any of the liver chemistry stopping criteria is met, do the following:

- Immediately hold IP. If on LA therapy, **do not** administer another injection until approval is received from the ViiV Safety and Labelling Committee.
- Report the event to the Medical Monitor within 24 hours of learning its occurrence (Section 7.4.3.4).
- Complete the liver event eCRF and SAE eCRF, where applicable, (see Section 7.4.3.4)
- Complete the liver imaging and/or liver biopsy eCRFs if these tests are performed.
- Perform liver event follow up assessments (described below), and monitor the participant until liver chemistries resolve, stabilize, or return to Baseline values as described below.
- Make every reasonable attempt to have participants return to clinic within 24 hours for repeat liver chemistries, liver event follow up assessments (see below), and close monitoring.
- A specialist or hepatology consultation is recommended.
- Monitor participants twice weekly until liver chemistries (ALT, AST, alkaline phosphatase, bilirubin) resolve, stabilize or return to within Baseline values.

Make every attempt to carry out the **liver event follow up assessments** described below:

Viral hepatitis serology including:

- Hepatitis A immunoglobulin M (IgM) antibody;
- Hepatitis B surface antigen (HBsAg) and Hepatitis B Core Antibody (IgM);

- Hepatitis C RNA;
- Hepatitis E IgM antibody;
- Cytomegalovirus IgM antibody;
- Epstein-Barr viral capsid antigen IgM antibody (or if unavailable, obtain heterophile antibody or monospot testing);
- Syphilis screening;
- Drugs of abuse screen including alcohol;
- Serum acetaminophen test (APAP adduct test). The site must contact GSK when this test is required. Please refer to the central laboratory manual.
- Blood sample for pharmacokinetic (PK) analysis, obtained within 60 hours of last dose. Record the date/time of the PK blood sample draw and the date/time of the last dose of investigational product prior to blood sample draw on the eCRF. If the date or time of the last dose is unclear, provide the participant's best approximation. If the date/time of the last dose cannot be approximated OR a PK sample cannot be collected in the time period indicated above, do not obtain a PK sample. Instructions for sample handling and shipping are in the SPM.
- Serum creatine phosphokinase (CPK) and lactate dehydrogenase (LDH);
- Fractionated bilirubin, if total bilirubin is greater than 1.5xULN;

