### 5.5.1.3. Liver Chemistry Stopping Criteria – Restart/Rechallenge

Participants who meet liver toxicity stopping criteria should not be retreated with investigational product unless an exemption has been approved by the ViiV Safety and Labeling Committee (VSLC). The guideline for Rechallenge/Restart approved by the VSLC, which is maintained as a separate document (See Section 12.3, Appendix 3) must be followed.

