#### **7.4.3.10. Grade 1 or Grade 2 Toxicity/Adverse Event**

Participants who develop a Grade 1 or Grade 2 AE or toxicity may continue study drug at the discretion of the investigator. Participants who choose to withdraw from the study due to a Grade 1 or 2 AE should have study withdrawal and follow-up evaluations completed.

**Participants who develop ALT  $\geq$ 3 times ULN while on study must consult with Medical Monitor prior to initiation or continuation of CAB LA + RPV LA**

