##### **7.4.4.1. Liver Chemistry Stopping and Follow-up Criteria**

Liver chemistry threshold stopping criteria have been designed to assure participant safety and to evaluate liver event etiology during administration of study drug and the follow-up phase. All Phase 3 participants who meet liver stopping criteria will be adjudicated by the ViiV Safety and Labelling Committee (VSLC) – resulting in a case

summary, adjudication, and management plan. The VSLC contains an external expert hepatologist, familiar with both DILI and cabotegravir, who will participate in this review. This committee meets on a 3-weekly basis, and can be convened on an ad hoc basis as needed.

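### The liver stopping rule for persistent ALT of 5 to <8xULN excludes symptomatic participants, so above a Baseline ALT of 1.67xULN a symptom can remove a stop that would otherwise apply.

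*Protocol*

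**What the plan says.** Section 5.5.1 lists six criteria, any one of which stops IP. In short form, with ALT and bilirubin in multiples of ULN:

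1. ALT ≥3 and bilirubin ≥2, with more than 35% direct. A note makes total bilirubin ≥2 a stop where the bilirubin testing is unavailable.
2. ALT ≥8.
3. ALT ≥3 with symptoms, if Baseline ALT is below ULN.
4. ALT ≥3 times Baseline, with symptoms.
5. ALT ≥5 and <8 for at least 2 weeks, with bilirubin below 2 "ULN & no signs or symptoms of acute hepatitis or hypersensitivity".
6. ALT ≥5 and <8 when weekly monitoring is not possible.

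Meeting a criterion has defined consequences:
- **Hold and work-up.** Section 5.5.1.1 requires IP to be held at once. Sites must not "administer another injection until approval is received from the ViiV Safety and Labelling Committee", and a fixed list of follow-up tests applies.
- **Adjudication.** Section 7.4.4.1: "All Phase 3 participants who meet liver stopping criteria will be adjudicated by the ViiV Safety and Labelling Committee". Section 5.5.1.2 also provides for a liver safety panel.
- **Discontinuation.** Section 5.5 makes it mandatory for "Liver toxicity where stopping criteria are met and no compelling alternate cause is identified".
- **Retreatment.** Section 5.5.1.3: "Participants who meet liver toxicity stopping criteria should not be retreated with investigational product" unless the committee grants an exemption.

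On entry, exclusion 30 bars only ALT of 3xULN or more. Exclusion 17 admits asymptomatic chronic hepatitis C under conditions, and Section 6.13.2 prohibits its treatment before Week 48.

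**The concern.** A stopping rule should not become weaker when signs of hepatitis appear. Criterion 5 is switched off by symptoms, which is safe only if criteria 3 and 4 catch every participant it releases. They do so when Baseline ALT is normal or mildly raised. They do not when Baseline is high enough that 3 times Baseline exceeds 5xULN. The eligibility rules admit such participants, and the Baseline-relative threshold in criterion 4 shows that raised Baselines were foreseen.

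At stake are the consequences tied to the Section 5.5.1 list. Drug-induced liver injury is a named risk in Section 4.8.1. The same section says cabotegravir can remain in the circulation for more than a year in some participants, so an injection given in error cannot be withdrawn.

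There is a second, lesser gap. An asymptomatic participant with total bilirubin ≥2xULN, shown by fractionation to be 35% direct or less, fails criterion 1 on the direct fraction and criterion 5 on bilirubin. This group is not necessarily sicker.

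**Working it through.** The plan states no figure to reproduce. The check applies the six criteria as written. All values are multiples of ULN; B is Baseline ALT.

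**Setting.** ALT from 5 to <8 for at least 2 weeks, weekly monitoring possible, and no bilirubin ≥2 that is more than 35% direct. Criteria 1, 2 and 6 are then not met.

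**Without symptoms, bilirubin <2.** Criterion 5 is met at every Baseline. On a grid of ALT 5.00 to 7.99 in steps of 0.01, all 300 of 300 points are stopped.

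**With symptoms.** Criterion 5 is not met. Criterion 3 needs B < 1. Criterion 4 needs ALT ≥ 3B. For B ≥ 1, no criterion is met when

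5 ≤ ALT < min(8, 3B).

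- The gap opens when 3B > 5, that is B > 5/3 = 1.67.
- It fills the whole band when 3B ≥ 8, that is B ≥ 8/3 = 2.67.
- Share of the band left uncovered = (min(8, 3B) − 5) / 3.

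| Baseline ALT | 3B | ALT range with no criterion met | Share of the 5 to <8 band |
|---|---|---|---|
| ≤1.67 | ≤5 | none | 0% |
| 1.8 | 5.4 | 5 to <5.4 | 0.4/3 = 13% |
| 2.0 | 6.0 | 5 to <6.0 | 1.0/3 = 33% |
| 2.2 | 6.6 | 5 to <6.6 | 1.6/3 = 53% |
| 2.5 | 7.5 | 5 to <7.5 | 2.5/3 = 83% |
| 2.67 to <3 | ≥8 | 5 to <8 | 100% |

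The bounds are the same if bilirubin is 2.5 at 20% direct.

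**Example.** Baseline 2.5, ALT 7 for two weeks, right upper quadrant pain, normal bilirubin, weekly visits:
- Criterion 1 fails on bilirubin.
- Criterion 2 fails because 7 < 8.
- Criterion 3 fails because Baseline is not below ULN.
- Criterion 4 fails because 7 < 3 × 2.5 = 7.5.
- Criterion 5 fails because of the pain.
- Criterion 6 fails because weekly monitoring is possible.

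Without the pain, criterion 5 stops IP.

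**Second gap.** Asymptomatic, bilirubin ≥2 and ≤35% direct: criteria 1 to 6 all fail across the whole band at every Baseline. If bilirubin cannot be fractionated, the note to criterion 1 makes it a stop and this gap disappears.

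**After deleting the parenthetical from criterion 5.** No grid point is left unstopped at two weeks in either gap.

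**The case against.** The strongest argument is about intent. Table 7 (Section 7.4.3.4) lists ALT ≥5xULN persisting two weeks with no symptom or bilirubin limit, and requires a liver event form within 24 hours. A site could read the parenthetical as meaning even in the absence of symptoms. That reading is possible, but it is not what the text says: the parentheticals in criteria 1 and 3 are plainly conditions, and criterion 5 has the same form. Table 7 governs reporting, not stopping. If the unrestricted rule was intended, the parenthetical should go for that reason alone.

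The second argument is that other rules cover the case, and they do reduce the risk:
- Section 4.8.1: "Participants will be withdrawn from CAB treatment where no compelling alternative cause is identified and DILI is suspected". This is a duty outside the stopping list and partly replaces the mandatory discontinuation. It also bars further injections in suspected hypersensitivity.
- Section 7.4.3.10: from ALT 3xULN, participants "must consult with Medical Monitor prior to initiation or continuation of CAB LA + RPV LA".
- Section 7.4.3.11: ALT of 5 to <10xULN is Grade 3 in Appendix 2. IP is withheld if the event is considered at least possibly related. Otherwise dosing may continue only on compelling evidence against IP and after discussion with the Medical Monitor.
- Section 7.4.4.13: IP stops for rash of Grade 2 or more with an ALT rise.
- Section 5.5.1.1: weekly follow-up from ALT 5xULN.
- Section 6.9.1: resumption must be discussed with the Medical Monitor in advance, so a restart is not unsupervised.

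In practice many of these participants would be held. But the rules rest mostly on a causality judgement or a consultation, and none triggers the committee hold, the fixed work-up or adjudication. The Grade 3 rule allows restart at Grade 2 or lower without the committee.

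Three further points stand. The affected group is narrow, because entry rules exclude cirrhosis, unstable liver disease and advanced hepatitis C. The second gap is weak on its own, since Gilbert's syndrome is allowed at entry. And the deletion still leaves the symptomatic participant in the example unstopped during the first two weeks; it only gives symptomatic and asymptomatic participants the same rule.

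**Conclusion.** The concern holds. As written, criterion 5 is inverted for participants with Baseline ALT above 1.67xULN: a symptom of hepatitis can take away a stop that would otherwise apply. From a Baseline of 2.67xULN the gap spans the entire 5 to <8xULN band.

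The conclusion assumes that the parenthetical is a condition, that weekly monitoring is possible, that ALT persists for at least two weeks, and that there is no bilirubin of 2xULN or more with over 35% direct. The Baseline range also assumes that Day 1 ALT stays near the Screening limit of <3xULN. The percentages are shares of an ALT range, not of participants. The protocol gives no Baseline ALT distribution, so the number affected cannot be estimated and is probably small. It should be corrected because it is a participant-safety rule for a long-acting drug and the correction is simple.

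**What to change.** In Section 5.5.1, delete the parenthetical on bilirubin and symptoms from the persistence criterion, so that ALT ≥5xULN and <8xULN for at least 2 weeks stops IP whatever the symptoms or bilirubin. Table 7 needs no change, because its row is already unqualified, and the two sections would then agree.

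The cost is one deletion and a few more holds and adjudications, including some participants with Gilbert's syndrome whose raised bilirubin is indirect.
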